1.1.2 Secondary Objectives

- To evaluate the safety and tolerability of the image guided, hypofractionated, focally dose escalated post-prostatectomy radiation.
- Estimate the rate of PSA control (biochemical progression free survival (bPFS) at 1 and 2 years after treatment with image guided, hypofractionated, focally dose escalated post-prostatectomy radiation).
- Describe the effects of image-guided, focally dose escalated prostate bed radiation on patient reported outcomes (SHIM, AUA Symptom Index, EPIC-26).

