3 STUDY IMPLEMENTATION

3.1 STUDY DESIGN

There will be two Arms in this trial. Arm 1 includes patients with rising PSA after prostatectomy for whom recurrent tumor has been visualized in the pelvis, providing a target for dose escalation. Arm 2 includes patients with rising PSA with no visualized tumor on imaging or patients with indications for adjuvant radiation after prostatectomy. Patients in whom MRI is contraindicated may enroll on Arm 2 if no evidence of disease is noted on other imaging modalities.

In Arm 1 radiation will be delivered to an escalated dose to areas of recurrent prostate cancer identified on imaging and a reduced dose will be delivered to the entire prostate bed.

In Arm 2 radiation will be delivered to the prostate bed only in patients for whom no recurrent tumor is visualized on imaging or if MRI imaging was contraindicated.

On Dose Level 1 treatments will be delivered in 20 fractions (approximately 4 weeks), on Dose Level 2 - in 15 fractions (approximately 3 weeks), on Dose Level 3 - in 10 fractions (approximately 2 weeks).

Abbreviated Title: Image guided radiation

Version Date: 06/03/2024

Treatment will be administered in daily fractions Monday through Friday except in the case of machine malfunction or federal holiday.

Daily image guidance with cone beam CT will be preferred. kV/kV imaging is allowed if the Cone beam CT imager is unavailable. An additional post-treatment cone beam CT after each fraction may be obtained to assess intrafraction motion.

Table 1 Fraction Dose Escalation Schedule

	Cohort 1, Arm1: Recurrent tumor visible, prostate bed with integrated boost		Cohort 2, Arm 2: Recurrent tumor NOT visible, prostate bed irradiation only	
Dose level	Dose to prostate bed	Dose to tumor	Dose to prostate bed	Dose to tumor
Level 1: 20 fractions	45.8 Gy in 2.29 Gy fractions	60.4 Gy in 3.02 Gy fractions	56.4 Gy in 2.82 Gy fractions	-
Level 2: 15 fractions	41.85 Gy in 2.79 Gy fractions	54.6 Gy in 3.64 Gy fractions	51.2 Gy in 3.41 Gy fractions	-
Level 3: 10 fractions	36.4 Gy in 3.64 Gy fractions	47.1 Gy in 4.71 Gy fractions	44.2 Gy in 4.42 Gy fractions	-

Serial PSA and serial correlative studies will be collected for two years post-treatment.

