6.3.1 Response Criteria

Biochemical control: Biochemical control will be defined as a post-radiation PSA that does not rise beyond 0.1 ng/dL.

Biochemical progression/biochemical failure: Serum PSA more than 0.1 ng/dL. At least 2 PSA measurements separated by 1 month are needed to confirm biochemical failure. If a PSA pre-

treatment was >0.1 ng/dL, a post-treatment value >0.1 ng/dL will not be considered biochemical progression if subsequent values continue to trend downwards after completion of radiation.

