6.3.2 Biochemical Progression-Free Survival

Biochemical progression free survival (bPFS) will be evaluated on this trial as a secondary endpoint. bPFS is defined as the duration of time from start of treatment to time of PSA progression or death, whichever occurs first. PSA progression (also known as biochemical failure) is defined based on elevation of PSA beyond 0.1 ng/dL. A total of 2 rising PSA values separated by at least 1 month are required to document biochemical recurrence. If the PSA remains elevated, the date of failure will be backdated to the first PSA measurement that exceeded 0.1 ng/dL. Only PSA values collected at the NIH Clinical Center will be used to evaluate disease status given the variability in ranges obtained in different laboratories.

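### Sections 6.3.1 and 6.3.2 define and date biochemical failure differently, and 8.3 leaves out early deaths, so bPFS at 1 and 2 years is not uniquely determined

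*Combined protocol and SAP*

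**What the plan says.** Event. Section 6.3.1 sets the threshold at 0.1 and states "At least 2 PSA measurements separated by 1 month are needed to confirm biochemical failure". It adds that, where the pre-treatment PSA was above 0.1, "a post-treatment value >0.1 ng/dL will not be considered biochemical progression if subsequent values continue to trend downwards". Section 6.3.2 sets the same threshold but states "A total of 2 rising PSA values separated by at least 1 month are required to document biochemical recurrence", with no exemption. Footnote 7 of the Study Calendar (3.3) points to 6.3.1 for the confirmatory measurement.

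Date. Only 6.3.2 gives one: "If the PSA remains elevated, the date of failure will be backdated to the first PSA measurement that exceeded 0.1 ng/dL".

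Time origin. Section 6.3.2: "bPFS is defined as the duration of time from start of treatment to time of PSA progression or death". Section 1.1.2 asks for "biochemical progression free survival (bPFS) at 1 and 2 years after treatment", and 8.1.2 uses the same phrase. PSA visits are counted from the end of radiation, every 3 months to month 24.

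Source. Section 6.3.2: "Only PSA values collected at the NIH Clinical Center will be used to evaluate disease status". Footnote 7 accepts outside laboratory results during follow-up and prefers, but does not require, confirmation at the NIH.

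Population and method. Section 8.3 makes a patient evaluable for biochemical relapse-free survival (taken here to mean bPFS) once he has a post-treatment PSA, first scheduled at month 3. Section 8.4.3 names Kaplan-Meier and gives no censoring rule.

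**The concern.** The 1- and 2-year bPFS rates are a secondary objective, and 8.1.2 expects them to compare favourably with published series. Such a comparison needs one rule for what counts as failure, when it happened and who is in the denominator, fixed before the results are seen. As written, two analysts who both follow the plan can classify the same patient differently, or date his failure on different sides of the 1-year landmark. In arms of at most 24 patients, a few such cases visibly change the reported rate.

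**Working it through.** The plan states no bPFS rate or precision, so there is no figure to reproduce. The check scores PSA series under each written rule, then sizes one reclassification.

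**Inputs.** Threshold 0.1 (6.3.1, 6.3.2); PSA at months 3, 6, ..., 24 after radiation (3.3); treatment lasting 2, 3 or 4 weeks (3.1); at most 24 patients per arm and 48 in total (8.2). The PSA series are constructed examples.

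**Event.** A PSA of 0.05, 0.05, then 0.15 at month 9 and flat afterwards:
- 6.3.1: two values above 0.1, not falling. Failure at month 9.
- 6.3.2, literally: 0.15 at month 9 rises from 0.05; the next value does not rise. Only one rising value, so no failure.

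**Date.** Pre-treatment PSA 0.5, then:

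| Month | 3 | 6 | 9 | 12 | 15 | 18 |
|---|---|---|---|---|---|---|
| PSA | 0.30 | 0.20 | 0.15 | 0.13 | 0.18 | 0.25 |

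- 6.3.2 literally: first value above 0.1, so month 3.
- 6.3.1 exemption carried over: the values at months 3 to 9 are still followed by lower ones and are exempt. Failure is dated month 12 (the nadir, followed by a rise) or month 15 (the first rise).
- The offset from start to end of treatment is 2/4.348 = 0.46 to 4/4.348 = 0.92 months. On schedule, the month-3 visit falls 3.46-3.92 months after the start and the month-12 visit 12.46-12.92. The patient has failed by 1 year on the literal date and is event-free at 1 year on either of the others. He has failed by 2 years on all three.

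**Consecutive values.** Neither section says whether the confirming values must be adjacent. In 0.05, 0.15, 0.14, 0.16 there are two rising values (months 6 and 12) only if they need not be. That looser reading also finds two rises in 0.30, 0.31, 0.20, 0.21, 0.12, 0.05 (pre-treatment 0.5), a series that declines and ends below 0.1.

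**Population.** A patient who starts radiation and dies before month 3 has an event under 6.3.2. With no post-treatment PSA, he is outside the 8.3 population.

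**Size.** One patient: 100/24 = 4.2 points in a full arm, 100/48 = 2.1 points overall. For scale, at the roughly 75% PSA control quoted in the Précis, the binomial standard error is sqrt(0.75 x 0.25/24) = 8.8 points per arm and sqrt(0.75 x 0.25/48) = 6.3 points overall.

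**Time origin.** Assume a constant hazard fitted to the progression-free survival the protocol cites: 80% and 62% at 5 years (1.2.1), 67% at 4 years (1.2.2). The monthly hazards are -ln(0.80)/60 = 0.0037, -ln(0.62)/60 = 0.0080 and -ln(0.67)/48 = 0.0083.
- With visits exactly on schedule, failures first seen at the month-12 visit cross the landmark: S(9) - S(12) = 1.1 to 2.3 points. At month 24, S(21) - S(24) = 1.0 to 2.1 points.
- Footnote 7 allows +/- 4 weeks at these visits. If visits are spread uniformly over that window, only those falling on or before the landmark from the end of treatment, but after it from the start, change side. That is a quarter of visits for a 2-week course and half for a 4-week course. Integrating over the window gives 0.2 to 1.0 points at 1 year and 0.2 to 0.9 at 2 years.

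**The case against.** The wording of 6.3.2 can be read more loosely. It also speaks of elevation beyond 0.1 and of a PSA that remains elevated; on that reading the flat series fails at month 9 in both sections. This is fair, and it is why the conflict is put as a literal reading. But the looser reading sets aside the word rising in the one sentence that states the confirmation requirement, and the plan does not say which prevails.

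Back-dating matters only for patients whose PSA was elevated before treatment. Adjuvant patients with undetectable PSA have no such decline. This stands. A reader might infer a shift of many points in the 1-year rate by supposing that every later failure had an earlier value above 0.1; the documents do not give that share.

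A reader might infer that the time origin is defined in two conflicting ways. Only 6.3.2 defines it; the objectives read as loose wording, and the effect is small once the visit windows are allowed for. It is a clarification.

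A reader might also infer that footnote 7 contradicts the NIH-only rule. It does not: 6.3.2 is categorical and gives its reason, while footnote 7 covers practical follow-up and prefers the NIH. What is missing is a censoring sentence. The bias from relapses documented only locally cannot be sized, because the documents do not say how many there would be or whether local follow-up is related to relapse.

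Finally, bPFS is descriptive, with no threshold or powered test, and one reclassified patient is smaller than the standard error. That limits the severity. It does not remove the contradiction, which is a matter of definition and does not shrink with better data.

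**Conclusion.** The concern holds for three things: the event definition, the dating rule and the exclusion of early deaths. The first rests on a literal reading of 6.3.2, the second applies only to patients with an elevated pre-treatment PSA, and the third follows directly from setting 8.3 beside 6.3.2. The assumption-free size is 4.2 points per reclassified patient in an arm of 24, or 2.1 in 48. How many patients would be affected, including deaths before month 3, cannot be derived from the documents.

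A reader might infer that the published rates would be biased in a known direction. The documents do not support this: requiring a rise, or leaving out early deaths, can raise the rates, while literal back-dating lowers the 1-year rate. The net direction is unknown. The MTD and the sample size do not depend on bPFS. The sponsor should correct this before bPFS is analysed.

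**What to change.** 1. Reconcile 6.3.1, 6.3.2 and footnote 7 into one event definition, chosen by the sponsor. It should say whether non-rising values above 0.1 count and whether the two confirming values must be consecutive.
2. State that the falling-PSA exemption applies to dating as well, so that failure is never dated to an exempt falling value.
3. In 8.3, analyse bPFS in all patients who start radiation, so that early deaths count.
4. Minor clarifications: say in 1.1.2 and 8.1.2 that the 1- and 2-year landmarks run from the start of treatment, as in 6.3.2. Keep NIH-only PSA as the primary source and add to 8.4.3 censoring at the last NIH PSA. Add a sensitivity analysis with outside PSA and locally documented relapses, because censoring a known relapse is informative.

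The cost is text changes and a little more analysis, with between-laboratory variability confined to the sensitivity analysis. Footnote 7 and the off-study criteria in 3.7.2 also refer to failure or recurrence, so the sponsor should check that the reconciled definition is applied consistently there.

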6.4 TOXICITY CRITERIA

The following adverse event management guidelines are intended to ensure the safety of each patient while on the study. The descriptions and grading scales found in the revised NCI Common Terminology Criteria for Adverse Events (CTCAE) version 4.0 will be utilized for AE reporting. All appropriate treatment areas should have access to a copy of the CTCAE version 4.0. A copy of the CTCAE version 4.0 can be downloaded from the CTEP web site (http://ctep.cancer.gov/protocolDevelopment/electronic_applications/ctc.htm#ctc_40).

7 NIH REPORTING REQUIREMENTS/DATA AND SAFETY MONITORING PLAN

7.1 DEFINITIONS

Please refer to definitions provided in Policy 801: Reporting Research Events found at: <https://irbo.nih.gov/confluence/pages/viewpage.action?pageId=36241835#Policies&Guidance-800Series-ComplianceandResearchEventReportingRequirements>.

7.2 OHSRP OFFICE OF COMPLIANCE AND TRAINING / IRB REPORTING

7.2.1 Expedited Reporting

Please refer to the reporting requirements in Policy 801: Reporting Research Events and Policy 802 Non-Compliance Human Subjects Research found at: <https://irbo.nih.gov/confluence/pages/viewpage.action?pageId=36241835#Policies&Guidance-800Series-ComplianceandResearchEventReportingRequirements>.

7.2.2 IRB Requirements for PI Reporting at Continuing Review

Please refer to the reporting requirements in Policy 801: Reporting Research Events found at: <https://irbo.nih.gov/confluence/pages/viewpage.action?pageId=36241835#Policies&Guidance-800Series-ComplianceandResearchEventReportingRequirements>.

7.3 NCI CLINICAL DIRECTOR REPORTING

Problems expeditiously reviewed by the OHSRP in the NIH eIRB system will also be reported to the NCI Clinical Director/designee; therefore, a separate submission for these reports is not necessary.

In addition to those reports, all deaths that occur within 30 days after receiving a research intervention should be reported via email unless they are due to progressive disease.

To report these deaths, please send an email describing the circumstances of the death to [contact] within one business day of learning of the death.

7.4 NIH REQUIRED NIH REQUIRED DATA AND SAFETY MONITORING PLAN

7.4.1 Principal Investigator/Research Team

The clinical research team will meet on a regular basis, at a minimum bi-weekly, when patients are being actively treated on the trial to discuss each patient. Decisions about dose level enrollment and dose escalation if applicable will be made based on the toxicity data from prior patients.

All data will be collected in a timely manner and reviewed by the principal investigator or a lead associate investigator. Events meeting requirements for expedited reporting as described in section [7.2.1](#) will be submitted within the appropriate timelines.

The principal investigator will review adverse event and response data on each patient to ensure safety and data accuracy. The principal investigator will personally conduct or supervise the investigation and provide appropriate delegation of responsibilities to other members of the research staff.

8 STATISTICAL CONSIDERATIONS

8.1 STATISTICAL HYPOTHESIS

8.1.1 Primary Objective

- Define the maximum tolerated dose (MTD) of image guided, hypofractionated, focally dose escalated post-prostatectomy radiation. Assessment of toxicities for dose escalation will occur through 3 weeks after radiation.

8.1.2 Secondary Objectives

- Define the toxicity profile of image guided, hypofractionated, focally dose escalated post-prostatectomy radiation. Assessment of acute toxicities for dose escalation will occur through 3 weeks after radiation.
- Describe the rate of PSA control (biochemical progression free survival, bPFS) at 1 and 2 years after treatment with image guided, hypofractionated, focally dose escalated post-prostatectomy radiation. We hypothesize that the rate of PSA control (bPFS) will compare favorably to the rate obtained with salvage radiation previously published series.
- Describe the effects of image-guided, focally dose escalated prostate bed radiation on patient reported outcomes (SHIM, AUA Symptom Index, EPIC-26). We hypothesize a reduction in quality of life (urinary and gastrointestinal) after radiation that persists for several months but returns to baseline in most patients by 2 years after treatment. We hypothesize that erectile dysfunction will progress without improvement over time.

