2 ELIGIBILITY ASSESSMENT AND ENROLLMENT

2.1 ELIGIBILITY CRITERIA

2.1.1 Inclusion Criteria

2.1.1.1 Patients must have histologically or cytologically confirmed adenocarcinoma of the prostate.

2.1.1.2 Indications for post-prostatectomy radiation exist:

- Disease progression (detectable PSA on two measurements obtained at least one month apart) or
- indications for adjuvant radiation exist (if undetectable PSA): pathologic T3, T4, N+ disease or positive margins (within 1 year of prostatectomy).

2.1.1.3 Age \geq 18 years.

Abbreviated Title: Image guided radiation

Version Date: 06/03/2024

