4.1 ADT

We will allow patients to receive ADT on this trial after enrollment if deemed clinically appropriate, as the bulk of data suggests that it has no impact on the toxicities we have defined as DLTs in this trial.

ADT will be delivered on this protocol as per the current standard of care with the duration of therapy to be determined by the treating physician if indicated. This may include an anti-androgen, gonadotropin releasing hormone agonist, or the combination of both. As an alternative, patients may also receive ADT through their local care provider (medical oncologist, primary care physician, urologist) in collaboration with the research team.

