8.2 SAMPLE SIZE DETERMINATION

The planned sample size is a minimum of 4 patients (2 per arm) and a maximum of 48 (24 patient's maximum per arm) based on the 3+3 design detailed in [3.1.2](#). An expansion of six additional patients can occur at the MTD in each arm as noted in [3.1.2](#). Estimates for sample size

are based on the assumption that all dose levels will accrue a maximum of patients, thus sample size is likely over-estimated. We anticipate accrual will require 30 months.

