8.4.3 Analysis of the Secondary Endpoint(s)

- Define the toxicity profile of image-guided, focally dose escalated prostate bed radiation in patients with a local or regional recurrence of prostate cancer after prostatectomy. All AEs except grade 1 with attribution to protocol treatment will be collected in tabulated way and analyzed.
- The rate of PSA control (biochemical progression free survival, bPFS) will be estimated by the Kaplan-Meier survival analysis and effects of clinical variables on bPFS will be assessed by the Cox proportional hazards model.
- The quality of life scores will be summarized at baseline and for each visit. Linear mixed effects model will be used to model quality of life scores at baseline and during and after treatment in which random intercept and random slope are used to account for patient-specific trajectory of quality of life scores. Changes of quality of life scores during and after treatment will be calculated from the estimated linear mixed effect model. The

similar analytical approach will be performed for depression scores and correlated with quality of life scores.

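### The bPFS population includes adjuvant and ADT-treated patients, so a favorable comparison with published salvage series could not be attributed to the radiation schedule

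*Combined protocol and SAP*

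**What the plan says.** The secondary hypothesis in section 8.1.2 is directional and its comparator is salvage treatment: "We hypothesize that the rate of PSA control (bPFS) will compare favorably to the rate obtained with salvage radiation previously published series". No series, benchmark rate or time point is named there.

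The enrolled population is wider. Section 3.1 says "Arm 2 includes patients with rising PSA with no visualized tumor on imaging or patients with indications for adjuvant radiation after prostatectomy". Section 2.1.1.2 admits the adjuvant patients with an undetectable PSA and sets no cap on their number. The other arm is salvage only: "Arm 1 includes patients with rising PSA after prostatectomy for whom recurrent tumor has been visualized in the pelvis". On hormone therapy, section 4.1 says "We will allow patients to receive ADT on this trial after enrollment if deemed clinically appropriate" and leaves the duration to the treating physician, within standard of care. The reason given is that ADT does not affect the DLTs; its effect on a PSA endpoint is not discussed.

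Sections 6.3.1 and 6.3.2 apply one PSA threshold to everyone, with no condition on indication or ADT. Section 8.3 makes a patient evaluable for biochemical control after a single post-treatment PSA. Section 8.4.3 then says "The rate of PSA control (biochemical progression free survival, bPFS) will be estimated by the Kaplan-Meier survival analysis". It states no strata, and adds a Cox model on clinical variables that are not listed.

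**The concern.** A rate from a mixed population is to be judged against salvage series. The protocol's own background says that two of the ingredients tend to raise PSA control. Section 1.2.1 notes that some candidates for adjuvant radiation would never have a PSA recurrence. It also reports that randomized salvage trials with or without ADT showed a benefit in progression-free or overall survival. Neither effect comes from hypofractionation or the focal boost.

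A third ingredient may act the other way: every Arm 1 patient has visible recurrent tumor.

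What is at stake is the reading of a stated secondary hypothesis. If the observed rate looks better than a salvage series, the plan offers no way to tell a good regimen from a different mix of patients and ADT use. An unfavorable result would be equally hard to read.

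**Working it through.** **Sample size, reproduced first.** Section 8.2 gives "The planned sample size is a minimum of 4 patients (2 per arm) and a maximum of 48". Three dose levels of 6 patients plus an expansion of 6, in two arms: (3 x 6 + 6) x 2 = 48, or 24 per arm. The minimum is 2 x 2 = 4. Both agree with the plan. If both arms fill, adjuvant patients can be at most 24/48 = 50% of the trial, but up to 100% of Arm 2.

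**Benchmarks.** The background gives 62-80% at 5 years for salvage (section 1.2.1) and 67% at 4 years for one hypofractionated series (section 1.2.2). Assuming a constant hazard, S(T) = S(t)^(T/t):

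| Published rate | 1 year | 2 years |
|---|---|---|
| 62% at 5 years | 90.9% | 82.6% |
| 80% at 5 years | 95.6% | 91.5% |
| 67% at 4 years | 90.5% | 81.9% |

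**Effect of the mix, with no treatment gain.** Let b be the benchmark, a the adjuvant share, d the ADT share among salvage patients, and hA and hD the hazard ratios of adjuvant and ADT-treated salvage patients against salvage without ADT. The mixed rate is

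a x b^hA + (1 - a) x [d x b^hD + (1 - d) x b].

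The documents give none of a, d, hA or hD, so all are assumptions.

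- Middle case at 2 years, b = 0.826, a = 0.25, d = 0.50, both hazard ratios 0.5, so b^0.5 = 0.909: 0.25 x 0.909 + 0.75 x (0.5 x 0.909 + 0.5 x 0.826) = 0.878. The shift is +5.2 points. The same inputs at 1 year give +2.8.
- Full range, a from 0 to 50%, d from 0 to 75%, hazard ratios (hA, hD) of (0.5, 0.5) or (0.25, 0.1), all three benchmarks: 0 to +6.7 points at 1 year and 0 to +12.7 at 2 years.
- Adjuvant mix alone at 2 years, hA = 0.5, a = 25% or 50%: +2.1 or +4.1 points on the 62% benchmark, +1.0 or +2.1 on the 80% benchmark. This is what remains if the comparator has the same ADT share, because the ADT part then cancels.

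**Is reporting by arm enough?** If half of Arm 2 is adjuvant, the last line applies to Arm 2 on its own: +2.1 to +4.1 points at 2 years with hA = 0.5. So it is not.

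**Counterweight from Arm 1.** Let half the trial be visible-tumor patients with an assumed hazard ratio of 1.5 to 2.0, with a from 0 to 50%, d of 0 or 50%, and hA = hD = 0.5. The net 2-year shift runs from -7.2 to +3.3 points. The low end is 0.5 x (0.826^2 - 0.826) = -0.072, with no adjuvant patients and no ADT.

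**Precision.** Treating the rate as a simple proportion, exact 95% limits are 72.2-93.9% for 41/48 and 62.6-95.3% for 20/24.

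**The case against.** The strongest reply is that nothing here is a formal comparison. Section 1.1.2 says estimate, section 8.1.2 says describe, and section 8.4.3 contains no external test. This is correct and limits the weight of the point, but section 8.1.2 still states a direction against salvage series.

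Second, the plan never says that the arms are pooled for bPFS. A reader might infer a single pooled rate from the absence of strata. That is an inference from silence, since by-arm handling is spelled out only for escalation and MTD. The point does not depend on it, because Arm 2 mixes indications by design.

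Third, the Cox model could include indication and ADT, and section 6.1.1 does collect ADT use. But neither is named as a covariate, a model within the trial does not alter the unadjusted Kaplan-Meier rate that would be compared, and few events can be expected in at most 48 patients.

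Fourth, a reader might infer that the rate is inflated, by something like 5 to 12 points. That size follows from taking the précis figure of about 75% as a 2-year rate without ADT, assuming 95% for adjuvant or ADT-treated patients, and mixing them: shares of 25%, 50% and 60% give 80%, 85% and 87%. The documents do not support this. The 75% has no time point and no ADT status, the 95% and the shares have no source, and visible-tumor patients may pull the rate down. The ADT part also depends on the comparator: the 62-80% figure is cited to a trial of salvage radiotherapy with or without short-term hormone therapy.

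**Conclusion.** The point stands as a limit on interpretation, not as a demonstrated upward bias. The 1- and 2-year rate can be raised by adjuvant patients, and by ADT if its use exceeds that in the comparator, and can be lowered by visible-tumor patients. Shifts of several points at 2 years are plausible with no effect of the regimen, but the sign is not fixed. Every hazard ratio, every share and the constant-hazard scaling above is an assumption; the documents fix only the mix that is permitted. As written, a favorable comparison could not be credited to the radiation schedule. This is a secondary, descriptive endpoint, and neither the MTD nor the sample size depends on it.

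**What to change.** In sections 8.1.2 and 8.4.3:

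- Restrict any comparison with salvage series to salvage patients: Arm 1 and the salvage part of Arm 2.
- Report Kaplan-Meier bPFS at 1 and 2 years with confidence intervals separately for Arm 1, Arm 2 salvage and Arm 2 adjuvant, and show the salvage results with and without ADT.
- Name the comparator series in advance, with its PSA definition, time point and ADT use. Otherwise drop the comparison and keep bPFS descriptive.

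A summary restricted to patients whose testosterone has recovered should not be added. It selects on a post-baseline event, and because recurrence is an off-study criterion in section 3.7.2, men who fail before recovery might never be seen to recover.

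The cost is SAP wording and a few tables. Indication is established at screening (section 2.2) and ADT use is recorded (section 6.1.1), so no new data are needed. The drawback is small groups: even a full arm of 24 with 20 controlled has an interval of about 63-95%, and the subgroups will be wider still.

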8.4 STATISTICAL ANALYSES

8.4.1 General Approach

This is a phase I study. There are two arms to this study for 1) patients with prior prostatectomy, rising PSA, and visible tumor on imaging, and 2) patients with prior prostatectomy with no visible tumor on imaging (rising PSA or indications for adjuvant treatment). Arms are enrolled and escalated separately. Dose level groups of 3-6 patients are evaluated at each dose level. The dose level on which 2 patients experience unacceptable toxicity is considered to have exceeded the MTD. The next lower dose level on which no more than 1/6 patients experience unacceptable toxicity is considered the MTD for each arm of the study.

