8.4.5 Exploratory Analyses

- Evaluate decision regret at the time of enrollment and at the end of follow up relating to the primary treatment for prostate cancer to determine if successful salvage mitigates decision regret. The percentage of patients scored as having decision regret will be compared to the percentage of patients not exhibiting decision regret (regarding the initial surgery). It is hypothesized the effective salvage therapy will mitigate decision regret expressed at the time of enrollment.
- Explore candidate biomarkers of radiation toxicity in blood and urine of patients receiving image-guided, hypofractionated, focally dose escalated post-prostatectomy radiation. Protein and metabolic biomarkers will be assessed in collected specimens.
- Explore MRI imaging parameters of erectile tissues in regards to testosterone and erectile dysfunction. MRI imaging of erectile tissue will be compared to evaluate for changes in volume and tissue characteristics after radiotherapy.
- To compare dosimetry of standard compared to biological optimization algorithms for treatment planning of post-prostatectomy radiation. Treatment planning will be optimized

with both approaches to allow comparison of normal tissue complication probability curves. Results will be reported in a descriptive fashion.

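### The plan hypothesizes that most patients regain baseline urinary and bowel quality of life by 2 years, but no planned analysis defines or estimates that proportion

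*Combined protocol and SAP*

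**What the plan says.** The objective in Section 8.1.2 is descriptive: "Describe the effects of image-guided, focally dose escalated prostate bed radiation on patient reported outcomes (SHIM, AUA Symptom Index, EPIC-26"). It carries a directional expectation for urinary and gastrointestinal quality of life, namely a reduction that "persists for several months but returns to baseline in most patients by 2 years after treatment". Neither *most* nor return to baseline is given a number.

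The analysis is in one bullet of Section 8.4.3. It has three parts:

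- "The quality of life scores will be summarized at baseline and for each visit", with the summary statistics not named.
- A linear mixed effects model, specified as follows: "random intercept and random slope are used to account for patient-specific trajectory of quality of life scores".
- An estimate of change taken from that fit: "Changes of quality of life scores during and after treatment will be calculated from the estimated linear mixed effect model".

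A percentage of patients is planned for one other questionnaire outcome, the exploratory one in Section 8.4.5: "The percentage of patients scored as having decision regret will be compared to the percentage of patients not exhibiting decision regret". There is no equivalent for the urinary and bowel scores.

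The Study Calendar (Section 3.3) collects questionnaires at baseline and every 6 months after treatment to month 24.

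**The concern.** The hypothesis concerns how many individual men are back to their own starting level at 2 years. The planned outputs are scores by visit and modelled changes in score. A correctly estimated average trajectory does not reveal how many men lie below their own baseline, because losses in some can be offset by gains in others, and a few large losses can pull down an average that is flat for everyone else.

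At stake is the reporting of a stated secondary hypothesis. As written, the authors would have to judge it from an average, or choose a definition of recovery after seeing the data. The average can mislead in either direction. Section 1.2.1 cites late Grade 2 or higher toxicity of about 25% (genitourinary) and 18% (gastrointestinal), so harm concentrated in a minority is plausible. That pattern would make a true hypothesis look false. A toxicity grade is not a questionnaire score, so this shows plausibility only.

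**Working it through.** **Inputs from the documents.** Maximum sample size: "a maximum of 48 (24 patient's maximum per arm) based on the 3+3 design detailed in" Section 3.1.2. Group size: "Dose level groups of 3-6 patients are evaluated at each dose level", with three dose levels per arm and an expansion of six (Sections 3.1 and 8.2). The documents give no SD, correlation, meaningful-change threshold, target proportion, alpha or power for quality of life. Every score change below is therefore an assumption.

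**Step 1: the plan's own figure.** 3 levels × 6 + 6 expansion = 24 per arm; 24 × 2 = 48. This reproduces the stated maximum.

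**Step 2: can a mean change decide the hypothesis?** Let a share f lose d points and the rest gain g points. The mean change is -f·d + (1 - f)·g.

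- f = 0.60, d = 10, g = 15: -6 + 6 = 0. The mean is back at baseline, but 60% are worse (for any threshold below 10 points), so the hypothesis is false.
- f = 0.20, d = 30, g = 0: -6 + 0 = -6. The mean is below baseline, but 80% are unchanged, so the hypothesis is true.

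The same mean can therefore go with either answer.

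**Step 3: how special is the first pattern?** A zero mean requires g/d = f/(1 - f). For a majority to be worse, the others' average gain must exceed the average loss: 1.22 times at f = 0.55 and 1.5 times at f = 0.60. That needs skew. If changes are normal with mean 0, the share worse by more than m baseline SDs is Φ(-m/√(2(1 - ρ))), where ρ is the assumed correlation between baseline and 24-month scores and the SD is taken as equal at both times. For m = 0.5:

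| ρ | share worse |
|---|---|
| 0.3 | 33.6% |
| 0.5 | 30.9% |
| 0.9 | 13.2% |

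With symmetric changes a zero mean always leaves a majority not worse, so it agrees with the hypothesis. The plan neither assumes nor checks symmetry.

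**Step 4: what would a direct estimate give?** The exact (Clopper-Pearson) 95% limits are the 2.5% quantile of Beta(x, n - x + 1) and the 97.5% quantile of Beta(x + 1, n - x).

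| Recovered | Proportion | Exact 95% CI |
|---|---|---|
| 34/48 | 71% | 56-83% |
| 17/24 | 71% | 49-87% |

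Showing more than 50% at one-sided 0.025 would need at least 32/48 or 18/24. If the true proportion is 70%, the power is 75% or 39%. These are best cases, because they assume that every enrolled patient has both forms. Section 3.2 limits questionnaires to English speakers, and Section 3.7.2 takes patients off study at recurrence.

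**The case against.** The strongest reply is that this is a phase I trial with MTD as its primary endpoint. The quality-of-life objective is to describe, and no error rate, power or escalation decision depends on it. That is correct and limits the consequence to reporting. It does not supply the missing estimate, and the remedy is itself descriptive.

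A second reply is that the plan offers more than an average: the visit summaries are unspecified and could include individual changes, and the random intercept and slope yield patient-level trajectories. A reader who infers that the plan produces nothing but mean change goes further than Section 8.4.3 does. But no use of either output to classify patients is stated. Visit-by-visit score summaries do not show change within a patient, and random-effect predictions are shrunk toward the average, which tends to understate the worst-affected men.

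A reader might also infer that a mean back at baseline would hide some 30-45% of men still impaired and so falsely confirm the hypothesis. The documents do not support this. Those shares depend on a threshold and a correlation that the documents do not give. They would also leave 55-70% not impaired, which is still most patients. A false confirmation needs the skewed pattern in Step 3, and nothing in the documents shows that it will occur.

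**Conclusion.** The mismatch stands: Section 8.1.2 states a hypothesis about a proportion of patients, and Section 8.4.3 neither defines return to baseline nor estimates that proportion. This rests on the text alone. That a mean change could mislead in either direction rests on the illustrative distributions in Step 2. How likely either pattern is cannot be judged from the documents. If changes are roughly symmetric, a mean near zero would agree with the hypothesis, though it still would not give the proportion or its uncertainty.

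The point is modest. It affects one secondary hypothesis in the final report and has no bearing on dose escalation or the MTD. It is worth correcting because the change is cheap and fixes the definition before the data are seen.

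**What to change.** Add to Section 8.4.3, alongside the mixed model:

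- **Estimate.** For each EPIC-26 urinary and bowel domain and the AUA-SI, give the proportion of patients whose 24-month score is no worse than their own baseline by more than a stated threshold, with an exact 95% CI, overall and by arm. Define worse in each instrument's own direction.
- **Baseline.** Use the last pre-radiation form. Study Calendar footnote 6 means that some patients receiving ADT have two earlier forms.
- **Threshold.** Fix it before analysis, for example half the baseline SD of that score. The documents name none, so the sponsor must choose and state it.
- **Denominator.** Main analysis: patients with both a pre-radiation and a 24-month form. Sensitivity analysis: all patients with a pre-radiation form, counting a missing 24-month form as not recovered, because recurrence is an off-study criterion in Section 3.7.2 and forms may be missing selectively.
- **Evaluability.** Do not restrict this analysis by the Section 8.3 rule, which requires quality-of-life measures at 3 months. The calendar schedules no questionnaire then, and the two sections must be reconciled.
- **Status.** Report the proportions descriptively, not as a test; the per-arm numbers cannot support one.

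The cost is one definition, one pre-stated threshold and one table, with no added visits, forms or patients. The downside is wide intervals, which should be shown as they are.
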